### Prior and concomitant therapy

Before the subjects start their first experimental trial, the health status of the subjects will be checked (Par-Q).

### Study analysis

#### *Sample size calculation*

Twelve subjects will be recruited to perform laboratory tests in a cross-over design. This amount of subjects is similar to the cohort size used in an earlier cross-over mental fatigue study concerning exercise (Martin et al., 2015).

#### *Analysis of the samples*

Physiological data gathering and analysis will be conducted by a PhD student of MFYS, [name] ([[contact]](mailto:[contact])). Ergospirometrical data will be gathered with the ergospirometrical device K5 from Cosmed and extracted to an Excel file using the program Omnia (Cosmed). Heart rate monitoring using Polar is a wireless and continuous process. Electro-physiological data (EXG, such as EMG, EEG) will be collected using Brain Vision Recorder (BrainProducts) and analysed using Brain Vision Analyzer (BrainProducts).

#### *Statistical analysis*

The physiological data will be statistically analysed with IBM SPSS statistics 25. Normality tests (Shapiro-Wilk normality testing) will precede parametric or non-parametric testing. Data

analysis of electro-physiological data will be conducted using Brain Vision Analyzer, wherein data will be pre-processed (signal filtering, re-referencing, artefact removal) and processed (power spectral analysis, coherence and non-invasive brain imaging). From Brain Vision Analyzer files will be extracted and inserted in standardized Low Resolution Brain Electromagnetic Tomography or sLORETA. The statistical analysis performed in sLORETA is Statistical non-parametric mapping or SnPM using the Fisher's permutation test that relies on a Bootstrap method with 5000 randomizations. [name] ([[contact]](mailto:[contact])) is responsible for the physiological data analyses.

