### Study design

The design of the study is interventional, cross-over (in laboratory conditions).

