#### Procedures

[figure not shown]
The physical and mental load of simulated industrial work will be investigated in laboratory conditions. Each subject will perform a pre-test and three lab trials. The pre-test (1h) will include basic biometric measurements, simple motor tasks (e.g. squatting), a dual-task walking task using the cognitive Stroop task to determine reaction time and accuracy during walking (Arcelin et al., 1998) and a familiarization trial of the simulated industrial task (described further down this protocol).

A first lab trial will include a cognitive task (90 min, 2-back task (Massar et al., 2010) (cognitive component). During a second trial a 90 minute walking task will be performed (physical component). The third trial will consist of a simulated industrial task (physical and cognitive component). The simulated industrial task will be a 90 minute task during which boxes (max 15 kg) will be moved from one place to another (0.05 Hz) while also performing a cognitive task (2-back task). Before and after the cognitive, physical or simulated industrial task a 10 minute Stroop task will be performed.

In the laboratory the ergospirometric device K5 (Cosmed) will be attached to the subject to measure oxygen consumption (via a mask) and indirectly energy expenditure. A heart frequency monitor (Polar) will be attached using a chest belt. The non-invasive electro-encephalography (EEG) and electro-myography (EMG) electrodes will be placed on the subjects head using non-invasive EEGcap and EMG surface electrodes, respectively. Furthermore, different questionnaires will be used, i.e. the Rating of Perceived Exertion (RPE), the Profile of Mood States (POMS), the Local Discomfort Scale, the Visual Analogue Scale (VAS) for fatigue, Nasa TLX, heat scores and Need for Recovery scale. In simulated industrial settings oxygen consumption and heart rates will be determined, as well as following questionnaires: RPE, POMS, Local Discomfort Scale, VAS for fatigue, Nasa TLX, heat scores and Need for Recovery scale.

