#### Flowchart

Twelve subjects will be included to conduct experiments in laboratory conditions. Three experimental trials per subject will be planned. One trial will include a simulated industrial task during which boxes are moved while walking on a treadmill. The intensity of the task will be determined based on the results of an ongoing observational study which ergonomically evaluates industrial work (approximated max 15 kg, lifting frequency of 0.05 Hz). During the second trial, a 90 minute normal walking task on a treadmill will be executed. The third trial will include a 90 minute cognitive task (2-back task). Before and after each trial a 10 minute Stroop task will be performed in order to analyse the cognitive performance of the subject. The total duration of one experimental trial is 3 hours.

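### Does describing the EEG test as both a permutation test and a bootstrap, with no contrast named, make the planned analysis unsound?

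*Combined protocol and SAP*

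**What the plan says.** The Statistical analysis section names the EEG test as SnPM by a Fisher "permutation test that relies on a Bootstrap method with 5000 randomizations". It lists the pre-processing steps and three kinds of output (spectral power, coherence, brain imaging). It does not say which conditions or time points are compared, at what level, or over which set of tests error is controlled.

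The design is given elsewhere. Sample size calculation: "Twelve subjects will be recruited to perform laboratory tests in a cross-over design". Flowchart: "Three experimental trials per subject will be planned", and "Before and after each trial a 10 minute Stroop task will be performed in order to analyse the cognitive performance of the subject". The Randomisation/blinding section randomises the order of the trials.

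Procedures places the EEG cap among the laboratory measurements. It later adds a second list: "In simulated industrial settings oxygen consumption and heart rates will be determined, as well as following questionnaires". EEG is not on that second list.

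**The concern.** A permutation test builds its null distribution by relabelling conditions. A bootstrap resamples subjects with replacement. The two can give different p-values at n = 12, and one sentence gives both names to one test. An analyst who took the word bootstrap literally would run something other than what SnPM implies.

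The design also admits several EEG contrasts: task against task, after against before within a trial, or that change compared between trials. With none named, two analysts could produce different maps, and a reader could not tell a planned map from one picked after the results were seen. The second measurement list raises the further question of whether the simulated industrial trial enters the EEG comparison at all. At stake are the type I error of the EEG results and the ability to reproduce them.

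**Working it through.** **Inputs.** From the document: n = 12 (Sample size calculation), 3 trials per subject (Flowchart), 5000 randomizations (Statistical analysis). Assumed, because the document is silent: two-sided 5% level, normal data, and for maps 100 voxels with correlation 0.3 or 0.5.

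**1. The figure of 5000.** It is a design choice and cannot be derived from other inputs, so the check is whether it is adequate.
- Pairwise contrast, signs flipped within subject: 2^12 = 4096 distinct relabellings. Since 5000 exceeds this, random draws repeat some, which is harmless. The smallest two-sided p is 2/4096 = 0.00049.
- Three conditions relabelled within subject: (3!)^12 = 6^12 = 2,176,782,336. Random sampling is the practical choice.
- Monte Carlo error at p = 0.05: √(0.05 × 0.95 / 5000) = 0.0031. At p = 0.01: √(0.01 × 0.99 / 5000) = 0.0014.

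**2. Error rate on the likely reading.** With 4000 simulated null datasets and one paired measure, type I error was 4.7% with all 4096 flips and 4.6% with 5000 random flips. Two separate simulations of the full enumeration gave 5.5% and 4.6%. The simulation standard error is √(0.05 × 0.95 / 4000) = 0.0034, so all are compatible with 5%.

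**3. Error rate on the literal bootstrap reading.**

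| Variant | One voxel | Maximum over 100 voxels (correlation 0.3 / 0.5) |
|---|---|---|
| Centred mean | 8.6% | 4.0% / 4.2% |
| Percentile | 8.7% | not run |
| Bootstrap-t | 3.8% | 1.2% / 0.3% |
| Sign flip, for comparison | 4.7% | 5.7% / 4.7% |

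The map runs used 600 datasets, so their standard error at 5% is √(0.05 × 0.95 / 600) = 0.0089, or 0.9 points. The centred-mean results cannot be told apart from 5%. Bootstrap-t is conservative, which would cost power rather than create false positives. The inflation is therefore a single-voxel result, whereas the plan describes mapping.

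**4. Contrast choice.** Chance of at least one false positive if every contrast is tested at an unadjusted 5% (200,000 runs of paired t-tests, n = 12, allowing for shared trials):
- one contrast: 5.0%
- three task pairs: 12.6%
- three before/after contrasts: 14.2%
- before/after plus between-trial change (six): 19.7%
- all nine: 29.8%

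Treating the tests as independent gives 1 − 0.95³ = 14.3% for three and 1 − 0.95⁶ = 26.5% for six. These values describe multiplicity in general. The document states neither the contrast families nor the unadjusted 5% level, so they do not measure an error in this plan.

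**5. Text set side by side.** Procedures counts the simulated industrial task as one of three laboratory trials and attaches EEG in the laboratory. The later list is not worded as exclusive, so reading it as removing EEG from that trial is strained. The timing of EEG recording cannot be judged, because the figure that opens Procedures is not shown in the text available for this review.

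**The case for a change.** The best argument for acting is that the wording is the smaller half. Software settles how a map is permuted, but it does not choose the contrast, the level or the family of tests. Nothing in the available text labels the EEG work exploratory, and naming contrasts would take only a few sentences.

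Part of this stands. The contrasts and level are indeed absent, and a report of the EEG results will have to state which maps were examined. But the same items are absent for heart rate, oxygen uptake, questionnaires and the Stroop task, so this is not a defect of the EEG test. Writing them down would record choices that the team must make anyway. It would not correct a wrong method, and whether to adjust across contrasts would still be the team's decision. It would also not make the test fully reproducible, since frequency bands, regions and the choice among the three outputs are open too.

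The argument about wording does not stand. SnPM, permutation and randomizations all point the same way, leaving one loose word. Within-subject relabelling follows from the cross-over, and the randomised trial order supports it for comparisons between trials.

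**Conclusion.** No change is needed. The word bootstrap is a slip of terminology. On the natural reading the test is valid, its simulated type I error is 4.6% to 5.5% against a nominal 5%, and 5000 draws are enough, so removing the word would alter no result. On the literal reading, the maps simulated with the maximum statistic gave at most 4.2%. That rests on assumed voxel numbers and correlations, normal data, and a maximum statistic that the plan does not name. With voxelwise testing and no correction, the single-voxel figures of 8.6% to 8.7% would be the relevant ones for the centred-mean and percentile variants.

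The missing contrast, level and scope of error control are a gap in detail that competent analysts fill from the three-period, before-and-after design. It matters for how firmly an EEG finding may be stated in a report, but no error rate can be attached to it without adding assumptions that the document does not make.

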### Quality control and quality assurance

To ensure data quality (heart rate and oxygen consumption) outliers will be detected and removed. Preceding the determination of oxygen uptake using the mobile ergospirometric device K5 the device will be calibrated to obtain accurate data. Additionally, a well fit mask will be used per individual (mask sizes range from extra-small, small, medium, large to extra-large). The latter will avoid leakage of air from the mask to the ambient air.

EEG electrodes are embedded in an EEGcap (different sizes from 54 to 60 (cm) according to head size). The electrical signal will be optimized using a gel between the electrodes and the skin of the subjects' head. Raw data will be recorded, but during recording the electrode impedance (indicator of signal quality) needs to be always kept below 10k $\Omega$ . Furthermore, during recording basic noise-reducing filters can be applied to allow the focus on the EEG frequency range of interest. The post-hoc pre-processing (basic filters and artefact removal) steps are performed by one researcher ([name]) and state-of-the-art pre-processing steps (such as Independent Component Analysis) are conducted to assure data quality.

### Data management

Questionnaires filled out during the experiment will be scanned in and digitalized. Physiological data will be measured by specific devices and stored locally on laboratory computers. After each experiment, the data will be restored on the investigators personal computer or external hard drive. The laboratory computer, as well as the investigators personal computer are embedded in a back-up loop which backs up twice a day to the laboratory's Synology NAS system.

### Publication policy

The publication policy of the research group is to publish papers in international peer-reviewed journals (preferably Q1 journals). All authors should have made substantial contributions to (1) the design of the study or acquisition of data or analysis and interpretation of data, (2) drafting the article or revising it critically, (3) final approval of the version to be submitted.

